3 STUDY DESIGN

This is a single-center, open-label, randomized controlled trial involving 20 eligible subjects who meet the inclusion/exclusion criteria. Subjects will be randomly allocated in a 1:1 ratio into two groups:

- Control Group: Standard CABG treatment only
- Cell Therapy Group: CABG + cellular transplantation (dose: 2 × 10⁸ cells) + perioperative immunosuppressive therapy

Postoperative Management:

All patients will undergo rigorous perioperative monitoring (within the first postoperative month) with comprehensive contingency protocols in place.

Follow-Up & Assessments:

Both groups will undergo identical follow-up evaluations at 1, 6, and 12 months, including:

Protocol (version 6.1)

Version data: 2021.08.01

Confidential
Page 17 of 38

Imaging studies (as per protocol), Laboratory investigations, Functional assessments. Documentation will be maintained via case report forms (CRFs) to ensure accurate and reliable data acquisition.

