4 STUDY TREATMENT

4.1 Treatment and dosage

4.1.1 Treamtment

All enrolled subjects will undergo standardized coronary artery bypass grafting (CABG) in accordance with established clinical guidelines. For patients in the cell therapy group, the treatment protocol incorporates myocardial cell transplantation alongside the standard CABG procedure. Following completion of graft anastomoses, a total of 2×10^8 allogeneic human regenerative cardiomyocytes are administered via epicardial injection at 10 sites surrounding the infarcted myocardial region.

Patients in the Cell therapy group were administered the following immunosuppressive regimen: intravenous immunoglobulin (2.5 g, IV) on preoperative day 1, intraoperative day (IOD), and postoperative day (POD) 3, combined with methylprednisolone (500 mg, IV) on preoperative day 1; rituximab (20 mg, IV) on IOD and POD4 to target CD20+ B-cell depletion; oral tacrolimus started preoperative day 3 and dose-adjusted to maintain trough levels within the target range of 3-5 ng/mL, as monitored by blood drug concentration until POD28, concurrently with mycophenolate mofetil (1 g, orally on preoperative day 1, increasing to 1.5 g/day until POD28) and prednisone (20 mg/day started IOD until POD28). The Control group did not receive any immunosuppressive medications. All study subjects

Protocol (version 6.1)

Version data: 2021.08.01

Confidential
Page 19 of 38

undergo intensive postoperative monitoring in the ICU with comprehensive emergency protocols implemented as needed.

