4.1.2 Dosage form and dosage

Cell Type: Allogeneic human regenerative cardiomyocytes

[figure not shown]
Dosage: A total of 2×10^8 cells are administered via intramyocardial injection, divided equally across 10 sites (250–500 µL per injection).

Administration: The procedure is performed intraoperatively following completion of graft anastomoses during CABG.

Control Group receive standardized CABG alone.

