5 STUDY PROCESS

5.1 Study Flowchart

5.2 VISIT AND ASSESSMENT SCHEDULE

All data collection procedures for this study are detailed in Table 3

Protocol (version 6.1)

Version data: 2021.08.01

Confidential
Page 20 of 38

Table 3 Visit and Assessment Schedule

	Baseline		Treatm	ent period		Follow-up			
Day (D) Month (M)	D-14 to D-1	D0	D1-D7	D14	D21	M1±7d	M6±14d	M12±14d	
Informed Consent	X								
Medical History and Physical Examination	X					X	X	X	
Vital Signs	X	X	X	X	X	X	X	X	
12-Lead ECG	X		X	X	X	X	X	X	
Concomitant Medications	X	X	X	X	X	X	X	X	
Coronary Angiogram	X								
(SYNTAX score)									
Cell transplantation documentation		X							
Echocardiography	X						X	X	
Cardiac MRI	X						X	X	
PET/ECT	X						X	X	
CT Scan (Chest/abdomen/pelvis)	X						X	X	
6 Minute Walk Test	X						X	X	
NYHA classification	X						X	X	
MLHFQ Score	X						X	X	
Holter Monitoring	X		X	X	X	X	X	X	
(24-hour ECG)									
Cardiac enzymes, troponin	X		X	X	X	X	X	X	
NTproBNP	X		X	X	X	X	X	X	
Complete Blood Count, Procalcitonin	X								
Blood type	X								
Biochemistry	X		X	X	X	X	X	X	
Urinalysis, Fecal Analysis	X					X	X	X	
Thyroid function tests (TSH, FT3, FT4)	X					X	X	X	
Tumor markers	X						X	X	
Immunogenicity	X			X		X	X	X	
Viral Serology	X			X	X	X	X	X	
Coagulation	X		X	X	X				
HLA Typing	X								
PRA	X					X	X	X	
DSA	X					X	X	X	
Cytokine Panel	X		X	X					

Protocol (version 6.1)
Version data: 2021.08.01

Confidential
Page 21 of 38

	Baseline	Treatment period				Follow-up		
Day (D) Month (M)	D-14 to D-1	D0	D1-D7	D14	D21	M1±7d	M6±14d	M12±14d
Adverse Events		X	X	X	X	X	X	X

Confidential Page 22 of 38

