6.5.3 Safety Analyses

Adverse events will be described using the preferred terms from the MedDRA terminology. All adverse events will be graded for severity according to the Common Terminology Criteria for Adverse Events (CTCAE), version 5.0. For Major Adverse Cardiac Events (MACE), including arrhythmias, and for other adverse events and adverse drug reactions distinct from arrhythmias, the number of events and the number of subjects experiencing these events will be determined. Adverse events assessed as Serious Adverse Events (SAEs) will be identified, and the number of such SAEs and the number of subjects experiencing SAEs will be determined. For significant events related to Coronary Artery Bypass Graft (CABG), the number of events and the number of subjects experiencing these events will be determined. Adverse events occurring during or within a specified period following the first administration of the investigational medicinal product will be summarized by CTCAE grade.

Clinical laboratory parameters, vital signs, and physical examination findings will be summarized according to study visit. The analysis will describe the observed values at each visit during the trial as well as the changes relative to baseline values.

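### The adverse-event summary by CTCAE grade is tied to first administration of the investigational product, which controls never receive, so as written it covers the cell arm only

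*Protocol*

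**What the plan says.** Protocol section 6.5.3 first provides for grading without restriction by arm or time: "All adverse events will be graded for severity according to the Common Terminology Criteria for Adverse Events (CTCAE), version 5.0". It then asks for numbers of events and of subjects for MACE, other adverse events and reactions, SAEs and CABG-related events, again with no time origin tied to the product. Only the summary by grade has one: "Adverse events occurring during or within a specified period following the first administration of the investigational medicinal product will be summarized by CTCAE grade".

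The control arm is described in section 3 as "Control Group: Standard CABG treatment only" and in section 4.1.2 as "Control Group receive standardized CABG alone". No sham or placebo injection is described. Section 4.1.1 adds: "The Control group did not receive any immunosuppressive medications".

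In the cell arm, section 4.1.2 times the injection as follows: "The procedure is performed intraoperatively following completion of graft anastomoses during CABG". Immunosuppression starts earlier, with "oral tacrolimus started preoperative day 3 and dose-adjusted to maintain trough levels" in section 4.1.1. The row "Adverse Events" in Table 3 (section 5.2) is marked at every column from D0 to M12 and is blank at baseline. The schedule is not split by arm.

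**The concern.** A selection rule based on time since first administration works when every patient receives the product. Here half of the patients are randomised to receive none. Taken at its word, the rule produces a severity table with no control column.

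That matters because everyone in the trial has major cardiac surgery, and adverse events of some severity are to be expected in both arms. Grade is one of the main ways to tell the ordinary course after CABG from excess harm, and the randomised controls are the reference for that reading. A cell-arm table alone cannot serve the purpose.

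The alternative is that the analyst supplies a start date for controls that the protocol does not give. The trial is open-label, so that choice could be made with allocation known. If controls were started at surgery and cell patients at injection, the two windows would differ, though only by the part of the operation before the injection.

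**Working it through.** The protocol gives no figure to reproduce on this point. The check is a count of the patients who can have the date that the rule requires.

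**Inputs**
- Allocation: 10 cell therapy and 10 control (section 6.3).
- Rule: the event occurs during, or in a period after, first administration of the product (section 6.5.3).
- Control exposure: no cells (sections 3 and 4.1.2) and no immunosuppression (section 4.1.1).
- Cell-arm exposure: immunosuppression from preoperative day 3; cells during surgery on D0, after the anastomoses (sections 4.1.1 and 4.1.2).
- Adverse-event collection: D0 to M12, one schedule (Table 3).

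**Step 1: who can enter the table.** The term investigational medicinal product is not defined, so both readings are taken.

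| Reading of the product | Controls with an anchor date | Cell-arm patients with an anchor date |
|---|---|---|
| Cells alone | 0 of 10 | at most 10 of 10 |
| Cells plus immunosuppression | 0 of 10 | at most 10 of 10 |

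The control result is the same on both readings. As written, at most 10 + 0 = 10 of 20 randomised patients can contribute.

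**Step 2: which cell-arm events can enter.** If the product is the cells alone, the window opens at the injection. Events earlier on D0 (anaesthesia, opening the chest, the anastomoses) are collected under Table 3 but do not qualify. If the product includes the immunosuppressive regimen, the window opens before surgery and no intraoperative event is excluded. This part is therefore conditional on the definition.

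**Step 3: what the rule does not touch.** Grading applies to all adverse events. The counts of MACE, other adverse events, SAEs and CABG-related events carry no product anchor. The primary endpoints, sustained ventricular tachycardia at 1 to 6 months and new tumours at 12 months, are timed from the operation (sections 2.2.1 and 6.5.1), which both arms undergo.

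**Step 4: effect of a common origin.** With the start of surgery on D0 as origin, 10 + 10 = 20 of 20 patients are eligible once operated on, and D0 events before the injection come in on either reading of the product. The data are already collected.

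**The case against.** The strongest reply is that this is one descriptive table and little hangs on it. The sentence names no between-arm contrast or test. It leaves the primary endpoints alone, and every control event is still recorded, graded and counted elsewhere. All of that stands, and it is why the point is not rated higher.

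A second reply is that the SAP, which is not at hand, can settle the details. That is right for the length of the window. A reader might infer that the unstated period is itself a defect, but a protocol may leave it to the SAP. The reply does not reach the anchor. That is a positive rule in the protocol, and an SAP that produced a two-arm table would have to depart from it.

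Three stronger readings are tempting and are not supported:
- A reader might infer that severity data for controls are lost. They are not; the events are only absent from this table.
- A reader might infer that section 6.5.3 contradicts itself. A narrower table beside unrestricted counts is not a contradiction, since both can be produced as written.
- A reader might infer that events before the injection are certainly excluded. That depends on the undefined product meaning the cells alone. Even then, the excluded interval is only part of one operation.

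It may also be said that the protocol does not rule out a further by-grade table covering both arms. That is true, but none is stated.

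**Conclusion.** The point holds as a should-fix. Followed as written, the one by-grade adverse-event summary that the protocol states includes 0 of 10 controls and at most 10 of 10 cell-arm patients. It is single-arm in a 1:1 randomised trial whose primary endpoints concern safety. This rests only on the wording of section 6.5.3 and the description of the control arm, and it does not depend on how the product is defined.

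The omission of cell-arm D0 events before the injection is secondary and assumes that the product means the cells alone.

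The consequence is confined to how severity is displayed. A two-arm severity table can be built from the data that the protocol already collects. Events before D0 are a separate matter: Table 3 does not mark adverse events at baseline, so a change of anchor within 6.5.3 neither causes nor cures that.

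**What to change.** Replace the sentence in section 6.5.3 with one whose time origin exists in both arms: adverse events will be summarised by treatment arm and CTCAE grade from the start of surgery (D0) through the month-12 visit. If a table timed from the product is also wanted, define the product and label that table as supplementary and cell-arm only. Any shorter windows, and the counting rule within patients, can be left to the SAP.

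Allocation should not be used as the origin while the text stands as it is. Section 6.4 has the envelope opened immediately before surgery, whereas section 4.1.1 starts cell-arm immunosuppression on preoperative day 3. Those two passages must be reconciled first.

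The cost is one sentence. No visit, assessment or data item is added, because Table 3 already collects adverse events from D0 to M12 on a single schedule.

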7 INFORMED CONSENT

Prior to any study-related procedures, all patients must provide written informed consent using the approved Informed Consent Form (ICF). The ICF has been reviewed and approved by the Ethics Committee. The informed consent process must be conducted in compliance with local laws and regulations. The content of the ICF must be understandable to the patient, and the patient has the right to have all questions regarding the study satisfactorily answered before signing. Consent must be voluntarily given by the patient without coercion. During the course of the study, if any amendments to the ICF are required, the revised form must be submitted by the Investigator to the Ethics Committee for review and approval. Newly enrolled patients must sign the most current, Ethics Committee-approved version of the ICF.

Confidential Page 24 of 38

8 RISKS AND CONTROLS

The primary risks to subjects participating in this study include immune-mediated rejection (graft-versus-host disease) associated with the administration of allogeneic-sourced regenerative cardiomyocytes, adverse effects related to the administration of immunosuppressive medications, and the potential occurrence of ventricular arrhythmias following cardiomyocyte transplantation

8.1 Tumorigenicity Risk and Control Measures for Allogeneic Human-Derived Regenerative Cardiomyocytes

Stem cells share several characteristics with tumor cells, including sustained proliferative capacity and resistance to apoptosis, as well as similar growth regulatory mechanisms. Animal models have demonstrated that human embryonic stem cells (ESCs) or induced pluripotent stem cells (iPSCs) can lead to both benign and malignant teratomas. However, the cellular product utilized in the present study consists not of stem cells, but of fully differentiated cardiomyocytes. Theoretically, this confers a substantially reduced tumorigenic risk, which is supported by the absence of tumor formation in prior small and large animal studies. Numerous international studies utilizing cardiomyocytes differentiated from mesenchymal stem cells (MSCs) report no definitive evidence of tumorigenicity associated with human MSCs, even beyond passage 50. Recent preclinical studies investigating allogeneic human-derived regenerative cardiomyocytes for heart failure treatment consistently report no teratoma formation following cell transplantation therapy [9,18,24-27]; relevant safety data are summarized in Table 1.

One of the safety assessments in this study involves monitoring for the incidence of newly developed tumors through scheduled CT scans and positron emission tomography (PET) examinations. The objective is to achieve timely detection and diagnosis to mitigate the severe consequences associated with tumor progression. Should any new tumor be identified, histopathological examination will be performed to definitively determine its origin and assess any potential association with the cell transplantation.

8.2 Graft-Versus-Host Disease Risk and Control

The presence of donor-derived T lymphocytes within the cellular graft carries a risk of eliciting a graft-versus-host response, which can manifest as a severe clinical condition known as Graft-Versus-Host Disease (GvHD). GvHD is classified based on the time of onset post-transplantation: occurrences within 100 days are designated as Acute GvHD, while manifestations arising after 100 days are classified as Chronic GvHD.

8.2.1 Acute GvHD

Acute GvHD, occurring early post-transplantation and representing a significant cause of early mortality, primarily affects the skin, gastrointestinal tract, and liver, with rare involvement of other organs. Cutaneous manifestations constitute the most frequent

presentation, characterized by erythema and maculopapular rash, often accompanied by pruritus or pain; lesions initially appear on the palms and soles, subsequently progressing to the face, ears, neck, trunk, and back, with severe cases demonstrating epidermal necrolysis and desquamation. Gastrointestinal involvement typically manifests as refractory diarrhea exceeding 1000 ml per day, associated with anorexia, nausea, and vomiting; advanced stages may feature abdominal pain with intestinal bleeding and obstruction. Hepatic involvement generally develops later, presenting as jaundice with elevated serum bilirubin and alkaline phosphatase levels. The majority of acute GvHD cases occur between 20 to 40 days following transplantation.

8.2.2 Chronic GvHD

Chronic GvHD typically manifests between 100 days and 1.5 years post-transplantation, with a minority of cases occurring up to 2 years. Incidence varies from 20% to 70% depending on graft source. Chronic GvHD frequently involves the oral mucosa, with xerostomia representing the earliest and most prevalent manifestation, often accompanied by oral pain or lichenoid mucosal changes. Cutaneous involvement initially presents as lichen planus-like lesions or polygonal papules, progressing in severe cases to generalized dermatopathy; late-stage skin changes include hyperpigmentation, atrophy, and fibrosis resembling scleroderma, potentially causing joint contractures and restricted mobility. Ocular involvement manifests as dry eye syndrome with significantly reduced tear production. Hepatic dysfunction is common, primarily evidenced by jaundice with histopathological findings of hepatic necrosis or cirrhosis. Gastrointestinal compromise frequently features esophageal pathology causing dysphagia and pain, potentially leading to weight loss; barium swallow studies demonstrate tapered esophageal strictures. Pulmonary involvement affecting bronchi and lung parenchyma may result in diminished pulmonary function and dyspnea. Additionally, Chronic GvHD is associated with immunodeficiency leading to recurrent infections, and persistent thrombocytopenia predisposing to hemorrhagic complications.

8.2.3 Treatment of GvHD

Standard first-line therapy for acute GvHD involves intravenous administration of methylprednisolone (a glucocorticoid), with potential dose escalation based on disease severity. Second-line therapy consists of one of the following agents: tacrolimus or mycophenolate mofetil; patients exhibiting suboptimal response to second-line therapy often receive combination therapy with methylprednisolone. Additionally, anti-T-cell monoclonal antibodies (e.g., anti-CD3 monoclonal antibody) may be utilized in patients refractory to methylprednisolone, while antibodies targeting the interleukin-2 receptor also demonstrate efficacy. For chronic GvHD, standard first-line therapy entails early initiation of prednisolone combined with azathioprine, followed by gradual tapering upon clinical improvement, with a total treatment duration of approximately one year. In cases accompanied by thrombocytopenia with reduced megakaryocytes in the bone marrow, prednisolone combined with cyclosporine A is preferred. Patients refractory to the

aforementioned therapies may receive second-line agents, including one of the following: tacrolimus or mycophenolate mofetil.

8.3 Immunosuppressive Medication Adverse Effects and Mitigation Strategies

The human immune system maintains highly sophisticated defense mechanisms against pathogenic agents, enabling the identification and targeted elimination of non-self entities including bacteria, viruses, foreign materials, allogeneic tissues, and synthetic implants. This complex immunological response represents a critical protective mechanism. Following allogeneic tissue or organ transplantation, the graft is recognized by the recipient's immune system as a non-self entity, triggering an immune-mediated attack that manifests as transplant rejection—a process involving graft destruction and clearance. Transplant rejection constitutes a primary determinant of graft survival. The administration of immunosuppressive medications represents an established therapeutic strategy for the effective prevention of transplant rejection.

Glucocorticoids: Adverse reactions associated with glucocorticoids are infrequent during short-term therapy but warrant vigilant monitoring. Potential adverse effects include: increased susceptibility to infections; drug hypersensitivity reactions; endocrine abnormalities; metabolic and nutritional disorders; gastrointestinal complications; skin and subcutaneous tissue disorders; musculoskeletal and connective tissue abnormalities; and menstrual irregularities.

Tacrolimus: This agent exerts its immunosuppressive effect primarily through inhibition of calcium-dependent signal transduction, thereby suppressing lymphokine production. A significant adverse effect is the inhibition of insulin secretion leading to hyperglycemia. Additional adverse reactions encompass hematological abnormalities; neurological manifestations; ophthalmic disturbances; tinnitus; respiratory disorders; gastrointestinal manifestations; renal impairment; dermatological effects; musculoskeletal complaints; and metabolic derangements.

Mycophenolate Sodium: This novel immunosuppressive agent employs a sodium salt substitution for the ester moiety present in mycophenolate mofetil, aiming to reduce gastrointestinal adverse effects associated with the ester group while maintaining efficacy in preventing transplant rejection. The most frequently reported adverse drug reactions include leukopenia and diarrhea. Additional potential adverse effects encompass infections; hematological abnormalities; headache; cough; gastrointestinal disturbances; abnormal liver function tests; elevated serum creatinine; and rash.

Basiliximab for Injection (e.g., Simulect): As an interleukin-2 (IL-2) receptor antagonist, basiliximab is associated with adverse reactions primarily including constipation, urinary tract infection, pain, nausea, hypertension, anemia, headache, hyperkalemia, hypercholesterolemia, surgical wound complications, weight gain, elevated serum creatinine, hypophosphatemia, diarrhea, and upper respiratory tract infection.

Safety Monitoring During Immunosuppressive Therapy: Subjects enrolled in this study will receive immunosuppressive therapy for a maximum duration of one month at reduced dosing levels. To mitigate the potential adverse effects associated with these agents, rigorous safety monitoring will be implemented throughout the dosing period. This includes scheduled assessments of hematological parameters, renal and hepatic function, quantitative immunoglobulin levels and lymphocyte subsets, as mandated by the protocol. Vigilant clinical monitoring for signs of adverse events or complications will be maintained. Prophylactic measures, including anti-infective prophylaxis and nutritional support, will be implemented per protocol-specified guidelines.

